#### 6.4.1 Laboratory

Laboratory values, incidence of high or low abnormal values, and shift from baseline with reference laboratory normal ranges, and summary statistics for laboratory values at each visit and changes from baseline (Baseline value is the last value before the first study drug infusion.) will be summarized.

#### 6.4.2 Adverse events

Individual listings of AEs (including age, AEs as reported, start, duration, severity, relation to study drug) will be provided.

For each AE, the number and percentage of subjects who experienced at least 1 occurrence of the AE will be tabulated according to the primary system organ class (SOC) and preferred term (PT) by age groups and overall study population combined.

Frequency tables, showing the number of subjects with drug-related AEs, SAEs, AE related to deaths, AE resulting in permanent discontinuation of study drug, and AESIs will be given.

An AE is defined as treatment-emergent if it started or deteriorated after the first infusion and not later than three days after the last infusion. The incidence of treatment-emergent AEs will be summarized using the Medical Dictionary for Regulatory Affairs (MedDRA).

Determination of whether or not an event is treatment-emergent will be derived after the missing or incomplete AE start date is imputed. In case an adverse event starts on the day of first administration of study drug and the time of onset is not known, the event is considered to be not treatment emergent, if it is reported to occur before the first dose of study drug. Details about imputation rules for missing and incomplete AE start are described in section 4.3.

In all other cases the event is considered to be treatment emergent. Inhibitors will be defined as treatment-emergent if they develop after first study drug application.

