**Intervention Groups and Duration:**

The study intervention will be used both for treatment and prevention of bleeding events and with surgical procedures. Individual participant dose decisions are at the discretion of the investigator.

**Part A:** All participants in Part A are expected to be treated for 6 months.

According to the Prescribing Information for KOVALTRY, dose regimens for prophylaxis are:

- Study participants  $\leq$ 12 years: 25 to 50 IU of KOVALTRY per kg body weight (given IV) twice weekly, three times weekly, or every other day according to individual requirements for 6 months
- Study participants  $>$ 12 to 65 years: 20 to 40 IU of KOVALTRY per kg of body weight (given IV) two or three times per week for 6 months

**Part B:** All participants in Part B are expected to be treated for 50 ED. Treatment in Part B may begin with start of prophylaxis with 15 to 50 IU/kg (minimum dose: 250 IU) at least 1 day a week; alternatively, prophylaxis can be started directly with a once-a-week schedule minimum dose of 250 IU for PUPs/MTPs of any weight. The starting dose may be tailored to the participant's weight or demonstrated bleeding tendency.

Study participants who develop high-titer inhibitor ( $>5$  BU/mL, confirmed by local laboratory) related to study drug, that interferes with effective treatment with FVIII, may opt to enter optional ITI treatment with study drug (Section 10.5.1) or leave the study and be treated with other therapies outside of the study at the discretion of the investigator. The optional ITI treatment with the study drug within the study requires a separate signed informed consent. Refer to Section 10.5 for additional details.

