#### 9.4.1 General Considerations

There is no confirmatory comparison planned for this study; study results will be numerically evaluated and compared with the data in the completed LEOPOLD Clinical Trials.

Efficacy analyses outlined in this section only include the data from Part A or Part B (i.e., data from the Optional ITI Treatment are excluded).

For the efficacy endpoints, bleeding events will be presented as summary statistics by age groups.

The annualized bleeding rates for each participant are estimated via

$$\text{Annualized bleeding rate [per year]} = \frac{365.25 \text{ [days per year]} \times (\text{\# of bleeding episodes in treatment period})}{\text{duration of treatment period [in days]}}$$

The treatment period is defined as from the date and time of first study treatment until the date and time of last infusion of study medication, or last visit, whichever is later (not including the Optional ITI Treatment). Before this period is the screening period, after this period is the follow-up period.

Further, for the derivation of analysis variables for bleeding episodes, the following rules will apply:

- “24-hour rule”:  
No more than 1 bleeding episode in a calendar day is counted. If there is more than 1 bleeding episode in a calendar day, to determine which bleeding episodes are counted, priority is given to treated bleeding episodes, spontaneous or trauma bleeding episodes, then joint bleeding episodes. Otherwise, the first bleeding episode in the day is counted. Severity and treatment response will be the worst value of the bleeding episodes of the day. The bleeding site will be aggregated over all bleeding events from that day.
- “72-hour rule”:  
A spontaneous joint or spontaneous muscle bleeding episode will not be counted if it occurs within 72 hours of a prior bleeding episode (or infusion for that bleeding episode) at the same site. For a bleeding episode to be affected by this rule, all sites listed for the bleeding episode must be the same sites specified in the previous bleeding episode. If the current and previous bleeds are both skin/mucosa bleeds, this rule does not apply. Infusions for such bleeding episodes will be considered to be follow-up infusions.

Missing information on date and time of bleeding episodes will be substituted by the date and time of first treatment, if available.

Further handling of missing data will be described in the SAP.

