### **1. Clinical Trials Experience**

The safety profile of KOVALTRY was evaluated in 193 previously treated patients (PTPs) (inclusive of 51 pediatric patients  $<12$  years of age) with at least three months of exposure to KOVALTRY. The safety analysis was done using a pooled database from three multi-center, prospective, open-label clinical studies. The median time on study for patients  $\geq 12$  years of age was 372 days with a median of 159 exposure days (EDs). The median time on study for patients  $<12$  years of age was 182 days with a median of 73 EDs. Subjects who received KOVALTRY for perioperative management (n=5) with treatment period of 2 to 3 weeks and those who received single doses of KOVALTRY for PK studies (n=6) were excluded from safety analysis. Table 3 lists the adverse reactions reported during clinical studies. The frequency, type, and severity of adverse reactions in children are similar to those in adults.

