### 4. General Statistical Considerations

#### 4.1 General Principles

There is no confirmatory comparison planned for this study, study results will be numerically evaluated.

Part A and Part B will be analyzed separately, both for efficacy and safety. The optional ITI treatment period will only be considered for the safety analysis.

The efficacy and safety analysis will be presented as summary statistics by age groups (<12 or  $\geq 12$  years of age) in Part A.

The statistical evaluation will be performed by using the software package SAS release 9.2 or higher (SAS Institute Inc., Cary, NC, USA). All variables will be analyzed by descriptive statistical methods. The number of data available and missing data, mean, standard deviation, minimum, quartiles, median, and maximum will be calculated for metric data. Frequency tables will be generated for categorical data.

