### 6.4.3 Adverse Events of Special Interest (AESI)

The adverse events of special interest in this study are:

- *Development of factor VIII inhibitors.*

Inhibitor development as measured by Nijmegen-modified Bethesda assay will be summarized by time point and presented in participant listings. The purpose of the listing is to delineate the clinical factors which may be positively associated with development of the inhibitor. Confirmation of the first positive inhibitor titer ( $\geq 0.6$  BU/mL) which is developed during the treatment with study drug will require repeat measurement of a second different sample. If the repeated inhibitor result is  $< 0.6$  BU/mL without intervention, the inhibitor is not confirmed and should not be reported as an SAE.

Inhibitors will be classified as being either low titer ( $\geq 0.6$  BU/mL and  $\leq 5$  BU/mL) or high titer based upon persistence of an inhibitor  $> 5$  BU/mL. Proportions of participants with inhibitor will be presented in an overview table. Exact Clopper Pearson CI for the proportion will be given if any inhibitor exists.

- *Hypersensitivity and allergic reactions including skin related and systemic reactions, such as anaphylactic reactions, (seriousness should be a case by case decision)*

The incidence of AEs, and AESI will be summarized and described for each age group and also for the overall study population combined.

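### Adverse events are summarised only by numbers and percentages of participants affected, while those aged 12 and over are followed for about half as long as in LEOPOLD, the trials named for comparison

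*SAP*

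**What the plan says.** **Adverse-event measure.** SAP 6.4.2 states that "the number and percentage of subjects who experienced at least 1 occurrence of the AE will be tabulated", by system organ class and preferred term. Its further tables (drug-related events, serious events, deaths, discontinuations, events of special interest) also count subjects. SAP 6.4.3 adds: "The incidence of AEs, and AESI will be summarized and described for each age group and also for the overall study population combined". An event is treatment-emergent "if it started or deteriorated after the first infusion and not later than three days after the last infusion", so time at risk follows treatment duration.

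**Comparator.** The study has no control group. Protocol 9.4.1 says "study results will be numerically evaluated and compared with the data in the completed LEOPOLD Clinical Trials", without limiting this to efficacy. The synopsis expects both the efficacy and the safety results to support LEOPOLD. SAP 4.1 is shorter and does not name LEOPOLD: "There is no confirmatory comparison planned for this study, study results will be numerically evaluated".

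**Follow-up.** The protocol synopsis says: "All participants in Part A are expected to be treated for 6 months". In the label attached as protocol section 12 (Clinical Trials Experience), the median time on study for LEOPOLD participants aged 12 and over is given as "years of age was 372 days with a median of 159 exposure days (EDs"; for those under 12 the text reads "years of age was 182 days with a median of 73 EDs".

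**Bleeding, by contrast.** Protocol 9.4.1 and SAP 4.5 annualise bleeding counts, and SAP 6.2.2 adds a negative binomial model with treatment duration as offset. SAP 6.1.2 summarises days in study and exposure days, but they are not used as a denominator for adverse events.

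**The concern.** The percentage of participants with at least one event grows with observation time. When two studies have different follow-up, their crude percentages differ even if the underlying event rates are equal. The plan handles this for bleeding but not for harms.

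The mismatch lies in one place: adolescents and adults in Part A, observed for about half as long as their LEOPOLD counterparts. Their percentages would be expected to come out lower for that reason alone. The results are meant to support licence renewal in China, and a lower figure could be read there as equal or better tolerability. The label's own LEOPOLD safety table reports subjects as n (%), so a side-by-side reading of like-looking columns is a natural use of the SAP tables.

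**Working it through.** **Inputs**
- Part A treatment: 6 months = 365.25/2 = 182.6 days (protocol 1.1).
- LEOPOLD median time on study: 372 days (159 exposure days) at 12 and over; 182 days (73 exposure days) under 12 (protocol 12, label).
- LEOPOLD pooled safety N = 193, of whom 51 were under 12, leaving 142 aged 12 and over (same place).
- Part A: 30 children and 12 adolescents/adults (protocol 9.2.1).

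**1. The comparator's measure.** The label gives headache as 14 subjects, 7.3%. Check: 14/193 = 7.25%. This is a crude percentage of subjects, the same kind of measure as in SAP 6.4.2.

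**2. Follow-up ratio, LEOPOLD to Part A**
- Aged 12 and over: 372/182.6 = 2.04. With the ±7-day window on the final visit: 372/189.6 = 1.96 to 372/175.6 = 2.12.
- Under 12: 182/182.6 = 1.00.
- In exposure days, for those treated two or three times weekly for 26 weeks: 52 to 78, against 159 in LEOPOLD at 12 and over.

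**3. Effect on the percentage at 12 and over.** Suppose the event-time distribution is the same in both studies. If a proportion p is affected by 372 days, the proportion affected at 6 months is

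p(6 m) = 1 − (1 − p)^[(182.6/372)^k],

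where k is the Weibull shape: k = 1 is a constant hazard, k < 1 early onset, k > 1 late onset. The documents give no onset pattern, so k is assumed and shown as a range.

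| p at 372 days | k = 0.5 | k = 1 | k = 1.5 |
|---|---|---|---|
| 7.3% | 5.2% | 3.7% | 2.6% |
| 30% | 22.1% | 16.1% | 11.5% |
| 50% | 38.5% | 28.8% | 21.2% |
| 70% | 57.0% | 44.6% | 33.9% |

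Every entry is below p. The 7.3% row is only an illustration, because the label's figure is pooled over ages. At 50% with k = 1, the expected count among 12 participants falls from 6 to 12 × 0.288 = 3.5.

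**4. Sampling error at n = 12.** The exact 95% interval for 1/12 is 0.2% to 38.5%, and for 6/12 it is 21.1% to 78.9%. The shift is therefore one of expectation and would not stand out from chance in a single small group.

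**5. The pooled column.** Using medians in place of means (an assumption), LEOPOLD follow-up is about (142 × 372 + 51 × 182)/193 = 322 days, a ratio of 322/182.6 = 1.76. But children make up 30/42 = 71% of Part A and 51/193 = 26% of LEOPOLD. Any difference in this column mixes follow-up with age.

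**The case against.** The strongest reply is that no adverse-event comparison with LEOPOLD is specified. The basis is one general sentence in protocol 9.4.1; the safety section, 9.4.4, does not mention LEOPOLD, and SAP 4.1 leaves it out. The study is descriptive, the 12 older participants were sized for PK, and exposure is summarised, so a careful reader would see the difference in follow-up. This stands as a limit. A reader might infer that the SAP plans a biased safety comparison. It does not; the bias arises if the crude percentages are set side by side, which the protocol sentence invites and nothing in the SAP prevents.

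A reader might also infer that percentages would simply halve, or that a doubled event rate would look like no difference. Both need a constant hazard. With early onset the effect is clearly smaller, and the label describes adverse reactions as similar in children and adults despite their different follow-up. Age may confound that statement, but it gives no support for mechanical halving.

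Nor do the documents establish a net bias in this study's favour in the pooled column. Age mix also acts there, and patient-year rates would not remove it.

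Two gaps in the material remain. The label lists adverse reactions pooled over ages, not all treatment-emergent events for those aged 12 and over. The detailed table specifications are in a separate document (SAP 1) that was not available, so an exposure-adjusted table there cannot be excluded. The choice of measure still belongs in the SAP text.

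Extending patient-year rates to inhibitors or Part B is not justified. Protocol 6.6.2 ties inhibitor testing to exposure days, so calendar-time rates would vary with infusion frequency, and no follow-up mismatch is shown for Part B, which protocol 9.2.2 says was designed in line with LEOPOLD Kids Part B.

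**Conclusion.** The point holds for participants aged 12 and over in Part A, 12 of 42. Their follow-up is about half the LEOPOLD median (ratio 2.04), and taken alone this can only lower the expected percentage with at least one event. The direction of that component is certain. Its size depends on when events occur: 50% becomes about 29% with a constant hazard and between about 21% and 38.5% for the Weibull shapes considered. These figures assume equal hazards in the two studies and use the LEOPOLD median to represent each participant's follow-up.

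For uncommon events, sampling error in 12 participants exceeds the effect; it matters most for broad summaries such as any treatment-emergent event. Children under 12 are not affected when they complete the planned 6 months. The pooled column is unsuitable for comparison. This is a modest weakness in a descriptive study, worth correcting because the remedy is cheap.

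**What to change.** In SAP 6.4.2, keep the n (%) tables. For Part A, by age group, add two rates for any treatment-emergent event, drug-related treatment-emergent events and serious events: subjects with a first event per patient-year at risk, and events per patient-year.

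In SAP 4.1, restore the reference to LEOPOLD and state that any comparison of adverse events is made within age group, using these rates or LEOPOLD events cut at the first 6 months, and that the pooled column is not used for comparison. The 6-month cut needs no assumption about the hazard.

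Leave inhibitors as SAP 6.4.3 has them: by time point, and as a proportion with an exact interval.

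The cost is SAP wording and one extra table. Event start dates and days in study are already collected, and re-expressing or cutting the LEOPOLD figures uses the sponsor's own data. The drawback is that the older group contributes only about 12 × 0.5 = 6 patient-years, so its rates will be imprecise, and they assume a roughly constant hazard.

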#### 9.4.4 Safety Analyse(s)

Safety analysis will be performed separately for Part A, Part B, and Optional ITI Treatment.

Safety data will be summarized for all participants in the safety population for overall and by age groups respectively for Part A and summarized for Part B. Laboratory findings, AEs, concomitant medications, vital signs, and medical history data will be provided in participant listings. Laboratory values and vital signs will be summarized.

Individual listings of AEs (including age, AEs as reported, start, duration, severity, relation to study drug) will be provided. An AE is defined as treatment-emergent if it started or deteriorated after the first infusion and not later than three days after the last infusion in Part A or Part B. The incidence of treatment-emergent AEs will be summarized using the Medical Dictionary for Regulatory Affairs (MedDRA).

Inhibitor development as measured by Nijmegen-modified Bethesda assay will be summarized by time point and presented in participant listings. The purpose of the listing is to delineate the clinical factors that may be positively associated with development of the inhibitor. Confirmation of the first positive inhibitor titer (Bethesda  $\geq 0.6$  BU/mL) will require repeat measurement of a second different sample.

If the repeated inhibitor result is  $<0.6$  BU/mL without intervention, the inhibitor is not confirmed and should not be reported as an SAE. Inhibitors will be classified as being either low titer ( $\geq 0.6$  BU/mL and  $\leq 5$  BU/mL) or high titer based upon persistence of an inhibitor  $>5$  BU/mL. Proportions of participants with inhibitor will be presented in an overview table. Exact Clopper Pearson CI for the proportion will be given if any inhibitor exists.

The rate of inhibitor development will be summarized and described for both the pediatric and the adolescent/adult populations, and for the overall study population combined.

Safety analysis for optional ITI treatment is based on the ITI treatment set. Laboratory findings (inhibitor titer and recovery), AEs, concomitant medications, and EDs will be provided in participant listings. More details will be provided in the SAP.

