## 10.5 Appendix 5: Optional Immune Tolerance Induction Treatment

### 10.5.1 Optional ITI Treatment for Participants who Develop High-Titer Inhibitors During the Study

If the option to receive ITI with the study intervention is made, the participant will discontinue participation in either Part A or Part B and continue in the Optional ITI Treatment, during which ITI will be provided at a dose of up to 200 IU/kg daily for up to a maximum of 18 months or until failure. A separate signed informed consent is required.

Initiation of ITI therapy (ITI Visit 1) should occur no later than 4 weeks from the date of notification by the investigator of the high-titer inhibitor development. In patients with a peak inhibitor titer  $>10$  BU/mL, it is recommended to postpone initiation of ITI until the inhibitor titer drops to  $\leq 10$  BU/mL. It is recommended to monitor the inhibitor titer monthly. In patients with a peak inhibitor titer  $>10$  BU/mL who experience serious or life-threatening bleeding or have frequent mild to moderate bleeding and are being considered for bypassing agent prophylaxis, an earlier start to ITI may be considered to avoid the morbidity associated with ongoing bleeding.

Response to ITI therapy may be observed earlier than 18 months and is defined as having no detectable inhibitor based on Nijmegen assay ( $<0.6$  BU/mL) and FVIII recovery of  $>66\%$  of predicted value. Failure is defined as no response ( $<20\%$  decrease in the inhibitor level) within a 6-month period after the initial 3 months of ITI and in the absence of any infection. In case of failure, ITI should be discontinued, and the Early ITI Termination visit will occur.

During the Optional ITI Treatment, failure to adhere to follow-up visits as per protocol (see Section 10.5.2) will lead to discontinuation of ITI support.

At the investigator's discretion, the participant may stop ITI with study drug. The Early ITI Termination visit should be done if the decision is made by the investigator/participant to stop ITI prior to documented negative inhibitor titer.

For analysis of Optional ITI Treatment data, see Section 9.3, Section 9.4.1, and Section 9.4.4. Efficacy (ABR) will not be analyzed for ITI patients. Safety will be analyzed separately for the ITI treatment set.

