### 6.4 Safety

All safety analyses will be performed on the safety analysis set for overall and by age groups respectively.

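### The SAP's treatment-emergent window omits the protocol's limit to Part A or Part B and, as written, would admit adverse events from optional ITI into the Part A/B TEAE tables

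*SAP*

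**What the plan says.** The protocol keeps three safety analyses apart. Section 9.4.4 states: "Safety analysis will be performed separately for Part A, Part B, and Optional ITI Treatment". It adds: "Safety analysis for optional ITI treatment is based on the ITI treatment set", and names the ITI listings: inhibitor titer and recovery, adverse events, concomitant medications and exposure days. It leaves further detail to the SAP. Section 10.5.1 repeats the principle: "Safety will be analyzed separately for the ITI treatment set". Section 8 says the same. The treatment-emergent window in 9.4.4 closes "not later than three days after the last infusion in Part A or Part B".

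The SAP treats the same matter in five places:

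- Section 6.4.2: an event is treatment-emergent "if it started or deteriorated after the first infusion and not later than three days after the last infusion". No study part is named. A later sentence in that section makes all remaining events treatment-emergent.
- Section 4.1: "Part A and Part B will be analyzed separately, both for efficacy and safety". On ITI: "The optional ITI treatment period will only be considered for the safety analysis". It does not say which safety analysis.
- Section 6.4: "All safety analyses will be performed on the safety analysis set for overall and by age groups respectively".
- Section 5.1 defines an ITI treatment population for an analysis of ITI treatment. No output in section 6.4 refers to it.
- Section 4.5 excludes the optional ITI period from the treatment period used for the annualized bleeding rate. Section 6.4.2 has no matching exclusion.

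**The concern.** TEAEs are a stated safety endpoint in both parts, for an objective about prophylaxis and treatment of bleeding episodes. ITI is a different regimen: under protocol 10.5.1 it runs at up to 200 IU/kg daily for up to 18 months, and the ITI schedule (10.5.2) provides for recording bypassing agents. Adverse events are collected at every ITI visit, so if anyone enters ITI these data will exist and need a rule.

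If the window stays open until the last ITI infusion, a Part B table of TEAEs, SAEs or drug-related events could mix events under prophylaxis up to 50 exposure days with events under ITI. The latter would come only from the few participants with inhibitors. Two programmers working from the same SAP text could produce different tables, and the study is open-label, so a window chosen after ITI events have been seen would be post hoc.

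**Working it through.** The point rests on text; the arithmetic only shows its possible size.

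**1. Does the SAP rule reach ITI infusions?** ITI is given with the study drug (protocol 6.1 and 10.5.1). SAP 6.4.2 refers to the last infusion without naming a part. Read literally, an ITI entrant's last infusion is the last ITI infusion.

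**2. Does another SAP sentence close the gap?** Section 4.1 brings ITI time into safety, section 6.4 uses only the safety set, and section 6.4.2 contains no ITI exclusion. Section 5.1 defines an ITI population but does not route any adverse event output to it. In the SAP text itself, nothing closes the gap.

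**3. Length of the window for one ITI entrant.** Inputs: 6 months of treatment in Part A; 6 to 12 months to 50 exposure days for most of Part B (protocol 7.2.8); ITI of at most 18 months; 365.25/12 = 30.44 days per month; plus 3 days.

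| Time in Part A/B | Protocol window | Literal SAP window | Ratio |
|---|---|---|---|
| 6 months | 6 × 30.44 + 3 = 186 days | 24 × 30.44 + 3 = 734 days | 4.0 |
| 12 months | 12 × 30.44 + 3 = 368 days | 30 × 30.44 + 3 = 916 days | 2.5 |

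The day counts are upper bounds: ITI entrants leave Part A or B early, and 18 months is the ITI maximum. Any gap before ITI is ignored.

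**4. Is an ITI entrant plausible in Part B?** Protocol 9.2.2 gives at least 92% probability of one or more inhibitors among 6 participants for rates of 35% to 54%. This reproduces:

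- 35%: 1 − 0.65^6 = 92.5%; expected cases 6 × 0.35 = 2.1.
- 54%: 1 − 0.46^6 = 99.1%; expected cases 6 × 0.54 = 3.2.

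These are inhibitors of any titer. ITI requires a confirmed high-titer inhibitor related to study drug that interferes with treatment, and a decision to opt in. Neither the high-titer share nor the uptake is given, so an entrant is plausible but the number could be zero.

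**5. Part A.** Protocol 2.3.1 puts the inhibitor risk in previously treated patients below 1%. At 1%, the chance of any inhibitor among 42 is 1 − 0.99^42 = 34%, and of ITI entry less. The issue matters mainly for Part B.

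**6. Effect on the reported figure.** SAP 6.4.2 tabulates the number and percentage of participants with at least one occurrence. In Part B, one additional participant with a given event moves its incidence by 1/6 = 16.7 percentage points. A participant who already had that event before ITI adds nothing.

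**The case against.** A reader might infer that the SAP directs ITI events into the Part A/B tables. It does not: no SAP sentence says so. Section 4.1 can be read as restricting ITI data to safety, without assigning them to a part. Section 5.1 foresees a distinct ITI analysis. Under protocol 4.4 an ITI entrant discontinues Part A or B with an Early Termination visit, so in a Part B table the last infusion could be taken to mean the last Part B infusion. The catch-all sentence in SAP 6.4.2 follows text about onset on the first dosing day and may be meant only for that case. SAP 1 also places table and dataset specifications in separate documents that form part of the SAP. They were not available here and may hold a period flag. All of this stands. It limits the claim to what the wording permits; it does not supply the missing limit.

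A reader might also compare infusion days: 18 × 365.25/12 = 548 daily infusions for one participant at the ITI maximum, against 6 × 50 = 300 planned Part B exposure days, a ratio of 1.8. That is a ceiling, and it does not carry over to reported incidence, which counts participants and not events per exposure day.

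The SAP is based on protocol version 2.0, which was not available. The Amendment 2 change table lists no change to 9.4.4 but mentions editorial changes, so it cannot be confirmed that version 2.0 carried the limit. Either way, the SAP does not match the current protocol.

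Finally, the study is descriptive, the primary bleeding rate excludes ITI, and adverse event listings with start dates are planned, so a misallocation could be seen and corrected. This lowers the severity but leaves the conflict.

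**Conclusion.** The concern holds as a conflict between two definitions of a stated safety endpoint. The SAP's treatment-emergent definition, as written, would admit ITI-period events into the Part A/B TEAE tables, whereas protocol 8, 9.4.4 and 10.5.1 require ITI safety to be analysed separately. It is not shown that such events will be counted there.

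The size depends on how many participants with high-titer inhibitors choose ITI, which the documents do not state. With no entrant there is no effect. With entrants in Part B, each additional participant with a given event shifts its incidence by 16.7 percentage points, assuming 6 participants in the safety set. The conclusion assumes that the table and dataset specifications do not already restrict the window. This should be fixed before database lock.

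**What to change.** In SAP 6.4.2, end the window as the protocol does, "not later than three days after the last infusion in Part A or Part B", and add that the optional ITI period is excluded. Apply the same limit to the sentence that makes all remaining events treatment-emergent.

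In SAP 6.4, state that:

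- adverse events in the ITI period are presented separately on the ITI treatment population, with the listings named in protocol 9.4.4;
- events between the end of the Part A/B window and the start of ITI are listed as not treatment-emergent for Part A/B. This interval can exist because protocol 10.5.1 allows up to 4 weeks from notification to ITI start and recommends postponement for some participants.

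The sponsor should define the adverse event window for the ITI period itself. Protocol 9.4.4 gives neither a start point nor a closing rule for it, so any such window would be an addition and not something the protocol already prescribes.

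The cost is a few SAP sentences and one period flag in the adverse event dataset, with a check that the table and dataset specifications agree. No new data are needed.
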